Our research team recently completed a patient-centered deprescribing intervention (Shed-MEDS) that targeted older hospitalized adults that required ongoing post-acute care (PAC). The nurse-practitioner or pharmacist-led deprescribing intervention resulted in statistically significant reductions in total medications and the combined burden of anticholinergic and sedative medications as measured by the drug burden index. Reductions were achieved at the end of the intervention (at the time of PAC discharge), and up to 90 days following the end of the intervention. Despite these successes, we do not know the feasibility or effect-size of a similar intervention implemented in a memory care ALF for PWD and their proxies. Thus, we aim to perform a single-arm, repeated-measures within-subjects feasibility pilot of the Shed-MEDS deprescribing intervention among PWD experiencing polypharmacy and their caregivers at the Abe's Garden dementia care ALF. **Our overarching hypothesis is that implementing the Shed-MEDS deprescribing protocol within a dementia care ALF will be feasible and reduce medications without worsening the quality of life for PWD.**

**Specific Aim 1:** Determine the feasibility of implementing the Shed-MEDS deprescribing intervention among PWD residing in a dementia care ALF.

- Aim 1a. Family proxy acceptability will be measured via the revised Patient Attitudes Toward Deprescribing (rPATD) designed for surrogates and through documentation of barriers and enablers to deprescribing recommendations shared via proxy interviews.
- Aim 1b. Implementation of the Shed-MEDS intervention will be assessed by the proportion of deprescribing recommendations acceptable to primary prescribers and family proxies of PWD.

**Specific Aim 2:** Document the effects of the Shed-MEDS deprescribing intervention on medication burden among PWD.

- Aim 2a: Compared to a pre-intervention period, the Shed-Meds intervention will result in significant increases in the total number of medications deprescribed, as defined by terminations at the end of 90 days.

- Aim2b: Compared to a pre-intervention period, the Shed-Meds intervention will result in a significant decrease in the anticholinergic and sedative drug burden of prescribed medications at the end of 90 days.

**Specific Aim 3:** Document the effects of the patient-centered deprescribing intervention (Shed-MEDS) on the quality of life of PWD.

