## Study Design and Outcomes Overview

This is a single arm pilot and feasibility study to adapt the Shed-MEDS intervention to the memory care setting. The Shed-MEDS intervention is a multistep deprescribing protocol which considers patient and disease factors, life expectancy, goals of care, and appropriate treatment targets. Medication-specific factors such as drug-drug interactions, drug-disease interactions, and drug-specific safety profiles are also incorporated. Finally, patient preferences and primary prescriber input are key to final deprescribing actions by identifying the medications patients are willing to deprescribe and seeking their primary prescriber's agreement. In this intervention, deprescribing is defined as either stopping a medication or reducing the dose/frequency of a medication.

The primary study setting is two assisted living facilities (ALFs) with dedicated memory care units.

Eligible residents are ALF residents aged 65 years or older with a dementia diagnosis and experiencing polypharmacy as defined by 5 or more medications.

Primary Outcome is the number of medications deprescribed, either stopped or reduced dose, 90-days after intervention completion.

Secondary Outcome is the impact of deprescribing on behavioral symptoms of dementia and resident quality of life.

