### Outcomes

Aim 1: Descriptive statistics (counts and proportions for categorical variables and means and SDs for continuous ones) will be used to describe Demographics at baseline, as well as Feasibility outcomes in Aim 1 at each measurement.

Aims 2 and 3: All statistical tests will be two-sided, with alpha = 0.05. For Aims 2 and 3, we will be applying a within-subjects intervention design to estimate the effect size of Shed-MEDS deprescribing intervention on Medication and Quality of Life outcomes. This design takes advantage of the smaller sample size in this pilot intervention, with each subject's 3-month retrospective review serving as their own control, which also removes the between-subjects differences in each condition. For the Medications outcomes in Aim 2 and the Quality of Life outcome of BPSD in Aim 3a, changes during the intervention period will be modeled using GEE, where time (multiple indicators), intervention group (one indicator) and their interaction will form the predictors, controlling

for baseline demographics. Hypothesized differences between the intervention and control groups will be examined using appropriate linear contrasts. For the DEMQoL-Proxy in Aim 3a, we will use a two-sample t-test to compare measurements at baseline with the 90-day follow-up, which is robust against normality or heterogeneity of variance.

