## Data Analyses

Missing Data: We will examine the incidence of missing data for each outcome in Table 2. We acknowledge that although the missing data could be informative due to intervention-related death or surrogate decision, we will not have enough data to formally test it due to the extremely small number of anticipated attrition (<5).

Repeated measures: Barring study withdrawal or death, main outcomes including the total number of medications, Quality of Life, and Safety will be assessed at four time points (enrollment, 30, 60, and 90 days) for each participant. We account for the anticipated positive correlations using a generalized estimating equation (GEE) framework for each repeated outcome. Unlike the parametric generalized mixed-effects models, GEE imposes no mathematical model for data distribution, thus providing valid inference for a broader class of data distributions.

Limitations: There are a number of limitations that must be acknowledged in this pilot deprescribing study. The most apparent is the limited sample size. Although small, the sample size is sufficient to understand the primary feasibility aims of our study, applying Shed-MEDS in this novel population of PWD in an ALF. We have selected a within-subjects study design to maximize the power to estimate effect sizes on medication and quality of life outcomes for subsequent larger randomized trials. Without a concurrent, randomized comparator, there is a potential for time-related threats to validity, as we cannot control the effects of time on the outcomes. Furthermore, we would not be able to rule out carryover effects of earlier treatments on the outcomes.

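### The single-arm GEE carries an intervention-group term and interactions that the stated occasions cannot identify, names no 90-day contrast, and leaves the BPSD count windows undefined

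*Combined protocol and SAP*

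**What the plan says.** **Design.** The Study Design and Outcomes Overview states: "This is a single arm pilot and feasibility study". The Outcomes section of Statistical Considerations describes a within-subjects comparison, "with each subject's 3-month retrospective review serving as their own control".

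**Model.** For the Aim 2 medication outcomes and for BPSD in Aim 3a, the same section specifies a GEE in which "time (multiple indicators), intervention group (one indicator) and their interaction will form the predictors", adjusted for baseline demographics. It adds: "Hypothesized differences between the intervention and control groups will be examined using appropriate linear contrasts".

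**Occasions.** Table 1 has one column for the 3-month retrospective review, one for enrollment, one shared by the 30- and 60-day follow-ups, and one for 90 days. The repeated-measures paragraph of Data Analyses says the main outcomes "will be assessed at four time points (enrollment, 30, 60, and 90 days) for each participant". The retrospective review is not in that list.

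**Hypotheses.** Relative to a pre-intervention period, Aim 2a expects "significant increases in the total number of medications deprescribed, as defined by terminations at the end of 90 days". Aim 2b reads "Compared to a pre-intervention period, the Shed-Meds intervention will result in a significant decrease in the anticholinergic and sedative drug burden", also at the end of 90 days. The overview defines the primary outcome thus: "Primary Outcome is the number of medications deprescribed, either stopped or reduced dose, 90-days after intervention completion".

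**BPSD.** The Secondary Outcomes section defines BPSD as a tally of episodes found in nurses' notes and incident reports. Table 1 collects it for the retrospective review, at enrollment and at every follow-up. The visible text does not give the days each tally covers, a link function or an offset.

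**The concern.** A mean model with time, group and their interaction belongs to a trial in which both groups are observed at the same times. Here every resident passes through the same sequence, and the occasion alone decides whether a record is control or intervention. If group is a function of time, software will drop columns, or the analyst must choose a coding, and what is reported as the group effect then depends on that choice. The pilot is meant to supply effect sizes and guide power for a later multi-center trial, so the contrast should be fixed in advance.

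The BPSD question is separate. A count grows with the days observed. If a 3-month control total is compared with totals from shorter follow-up windows and no offset is used, an unchanged rate looks like improvement. Aim 3a is the aim meant to show that deprescribing does not make residents worse, so an error in that direction could hide worsening.

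**Working it through.** The plan gives no power or sample-size derivation, so there is no stated figure to reproduce. The checks are on the rank of the mean model and on expected count ratios.

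**1. Rank.** With T time levels, the model has 1 intercept + (T − 1) time indicators + 1 group indicator + (T − 1) interactions = 2T columns. Its rank cannot exceed the number of distinct time-by-condition cells observed.

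| Reading of the occasions | Columns | Cells | Rank | Group coefficient and interactions |
|---|---|---|---|---|
| Four (Data Analyses list) | 8 | 4 | 4 | none estimable |
| Five (Table 1, one retrospective record) | 10 | 5 | 5 | none estimable |
| Three monthly retrospective blocks matched to 30, 60, 90 days (assumed) | 6 | 6 | 6 | all estimable |

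The first two rows hold whether enrollment is coded as control or as intervention. Group stays aliased with time even if the interaction is removed. Baseline demographics do not help, because they are constant within a resident and every resident has the same occasion-to-condition mapping.

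**2. The Aim 2 contrast.** In the five-occasion reading, the 90-day mean minus the retrospective mean is estimable from the time indicators alone. In the four-occasion reading the retrospective review is not a model level, so the contrast does not exist.

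**3. What a workaround would do.** Suppose the single retrospective record is given the time label of one visit, a coding that no visible text describes. At most one group effect is then identified, and no interaction is. For illustration, take mean medication totals of 7.78 (retrospective), 7.78 (enrollment), 7.28, 6.78 and 6.28 (30, 60, 90 days). Only the starting 7.78 comes from the documents (the average at the first facility, under Study Setting); the rest are assumed. The group effect is:

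- paired with enrollment, coded as intervention: 7.78 − 7.78 = 0.0
- paired with 30 days: 7.28 − 7.78 = −0.5
- paired with 60 days: 6.78 − 7.78 = −1.0
- paired with 90 days: 6.28 − 7.78 = −1.5

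If enrollment is instead coded as control and paired with the retrospective record, the rank falls to 4 and no group effect is identified. The 90-day minus retrospective contrast is −1.5 under every rank-5 coding.

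**4. BPSD windows.** Take 3 months as 90 days. Without an offset, the count ratio = (follow-up days ÷ control days) × true rate ratio.

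| Days in follow-up total | Unchanged rate | Doubled | Tripled |
|---|---|---|---|
| 30 | 30/90 = 0.33 | 0.67 | 1.00 |
| 90 | 90/90 = 1.00 | 2.00 | 3.00 |

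A null simulation of a Poisson GEE with 30-day follow-up totals against a 90-day control gave a mean rate ratio of 0.32 and rejected in 100% of runs without an offset. With offset log(days) it gave 0.97 and 5.3%. Its inputs are assumptions, not from the documents: 36 residents, 3 episodes per 90 days on average, gamma frailty, exchangeable correlation, 300 runs.

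With equal windows only lost time remains. If the planned 10–15% attrition (4 to 6 of 40) falls evenly over 90 days, observed time is 1 − 0.10/2 = 0.95 to 1 − 0.15/2 = 0.925 of the full window.

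**The case against.** The strongest defence is that one Table 1 column need not mean one record. The 30- and 60-day visits share a column too, and the specified model makes sense if three control months are matched to 30, 60 and 90 days. Figure 1 and the footnote to the retrospective column are not in the copy reviewed and could say so. This stands as a qualification: under that reading the model is full rank. The visible text does not state it, and the plan should.

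The list of four time points may describe only the prospective assessments. That is fair, but the five-occasion reading has the same aliasing. The word groups may simply mean conditions. That is also fair, but the aliasing does not depend on the word.

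A reader might infer that the Aim 2 result is lost. The documents do not support this. Aims 2a and 2b state the comparison in words, and it is estimable with five occasions. The fault is that the analysis section does not specify it.

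A reader might also infer that the medications-deprescribed outcome suffers the same window bias as BPSD and that an increase would be understated. That is not supported either. The end of 90 days can be read as status at day 90, where no window applies. If the outcome is a count over a period, the 90-day and 3-month windows already match at the only time point the aim and primary outcome name. What remains open is which reading is meant and, for a period count, the day it opens, since orders are changed as the last intervention step (Final Deprescribing Actions).

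Finally, this is a pilot with no power claim, and its limitations concede that time effects cannot be controlled. That concession concerns confounding, not identifiability, and the plan still specifies two-sided tests at 0.05.

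**Conclusion.** The concern holds, with moderate confidence, as something that should be fixed. On the occasions in the visible text, the group coefficient and all interactions cannot be estimated (rank 4 of 8, or 5 of 10). This is algebra and does not depend on sample size, link or working correlation. It does depend on the retrospective review entering as one record or not at all; monthly blocks would remove it. The 90-day versus pre-intervention contrast is recoverable but is not named in the analysis section.

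The BPSD distortion is conditional. It is large, 0.33 for an unchanged rate, if follow-up totals cover 30 days, and small if windows are equal. The visible text does not settle which, and missing footnotes might. Total medications and the Drug Burden Index are point-in-time measures and are unaffected by window length.

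**What to change.** 1. Replace the group indicator and its interaction with occasion indicators: retrospective, enrollment, 30, 60 and 90 days (5 parameters, rank 5). If the review is abstracted in three 30-day blocks, say so and use period by month plus an enrollment indicator (6 + 1 = 7 parameters, rank 7). Do not simply add enrollment as a fourth time level to the existing model: that gives 8 columns of rank 7, and which coefficients are lost depends on the reference level. With enrollment as the reference, the group coefficient and all three interactions are lost.
2. Name 90-day follow-up versus the retrospective period as the contrast for Aim 2 and for BPSD. Delete the reference to intervention and control groups, and list the retrospective period among the occasions in Data Analyses.
3. For BPSD, state the days each count covers, and use equal windows or a log link with offset log(days observed).
4. For medications deprescribed, state whether the outcome is status at day 90 or a count over a period. Only if it is a period count, compare the 90-day window with the 3-month retrospective window and state the day the window opens.

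The cost is SAP wording, plus recording days observed from charts already being abstracted. No new visits or staff are needed.

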## Data Analyses

Missing Data: We will examine the incidence of missing data for each outcome in Table 2. We acknowledge that although the missing data could be informative due to intervention-related death or surrogate decision, we will not have enough data to formally test it due to the extremely small number of anticipated attrition (<5).

Repeated measures: Barring study withdrawal or death, main outcomes including the total number of medications, Quality of Life, and Safety will be assessed at four time points (enrollment, 30, 60, and 90 days) for each participant. We account for the anticipated positive correlations using a generalized estimating equation (GEE) framework for each repeated outcome. Unlike the parametric generalized mixed-effects models, GEE imposes no mathematical model for data distribution, thus providing valid inference for a broader class of data distributions.

Limitations: There are a number of limitations that must be acknowledged in this pilot deprescribing study. The most apparent is the limited sample size. Although small, the sample size is sufficient to understand the primary feasibility aims of our study, applying Shed-MEDS in this novel population of PWD in an ALF. We have selected a within-subjects study design to maximize the power to estimate effect sizes on medication and quality of life outcomes for subsequent larger randomized trials. Without a concurrent, randomized comparator, there is a potential for time-related threats to validity, as we cannot control the effects of time on the outcomes. Furthermore, we would not be able to rule out carryover effects of earlier treatments on the outcomes.

# DATA COLLECTION AND QUALITY ASSURANCE

## Data Collection Forms

Data is obtained from multiple sources including residents (or surrogates) directly via standardized interview protocols and electronic medical records. All assessments, both interviews and medical record reviews, are recorded on paper forms stamped by the Vanderbilt IRB. Hardcopy forms should use the participant's randomly assigned ID number. Utilizing case report forms allows for quality assurance reviews of data entered in the electronic (REDCap) databases.

## Data Management & Storage

All paper case report forms are maintained in a secure and locked file cabinet in a secure and locked office. Data collected from resident/surrogate assessment and medical records are entered directly into Research Electronic Data Capture (REDCap) databases. Use of REDCap outside the Vanderbilt server is allowable; however, it requires two factor authentication for security purposes. Assessment and interview forms are entered within the same week of data collection, and if possible, the same day.

Study coordinators will maintain SPSS databases for study tracking purposes. These databases along with data exported from REDCap for reporting and analysis purposes are maintained on a password protected VUMC secure server, which is only accessible to key study personnel registered with the IRB. Information in the REDCap databases and the secure server will be stored for an indefinite period of time to allow for subsequent data analysis and future reference.

## Quality Assurance

No quality assurance training or metrics are required beyond IRB training and VUMC confidentiality standards. To reduce data entry errors, the REDCap databases have been created in a longitudinal model to match the paper case report forms and including branching logic and automated syndrome scoring. Additionally, to ensure the integrity of the data, the data manager conducts weekly data reviews to check for both completion and accuracy.

## PARTICIPANT RIGHTS AND CONFIDENTIALITY

Shed-MEDS deprescribing intervention meets the criteria for human subjects research and, as such, is subject to a standard review by the institution's review board. All protocols, consent forms, and research materials were submitted to the Vanderbilt IRB. The study is subject to annual review by the IRB. In accordance with VUMC policy, all key study personnel complete human subjects training annually and Good Clinical Practice training every three years. Below is a description of the key human subjects materials submitted to the IRB.

### Rationale for studying a potentially vulnerable population

Patients with cognitive impairment or dementia represent a population at potentially increased risk for worsened outcomes associated with polypharmacy. Thus, it is important to understand the effect of deprescribing on this vulnerable population. Patients with moderate impairment will likely need a surrogate to provide consent and complete some study measures. Patients with mild impairment may (not) need a surrogate to provide consent. We will complete a “standardized evaluation to sign informed consent” for all eligible patients with cognitive impairment based on the BIMS (see *Recruitment and Informed Consent Procedures*). Based on the distribution of BIMS scores, we may examine intervention effects by cognitive status via sub-group analyses.

Patients with a history of seizures on and off antiepileptics who otherwise meet study eligibility criteria will be considered eligible for enrollment. Antiepileptic medications are commonly used in the treatment of non-epileptic conditions. Although, the presence of a seizure disorder will not be a contraindication to deprescribing, patients who are currently on a therapy specifically for this indication will be continued on antiepileptic medications and managed by the medical team, as per usual care practice.

### Approach to potential risks of the proposed study

The proposed research study has been designed based on input of experts in geriatrics, pharmacology, psychiatry, LTC nursing and medicine, and clinical trials. In order to assure appropriate research subject selection and high quality data collection, all study personnel will undergo training in the study protocol. Exclusion criteria have been carefully considered to help minimize patient risk prior to enrollment. In addition, our deprescribing intervention protocol is a carefully developed, multi-stage process that includes the independent review of multiple clinicians, each of whom has the ability to stop any recommended deprescribing action. This includes the study nurse practitioner, the facility medical team, the outpatient prescribing clinician, as well as the patient/surrogate. Each recommended medication for deprescribing will be considered for its potential for physiologic withdrawal, pharmacokinetic/pharmacodynamic effects, and medical condition exacerbation. For each medication for which any one of these is a potential concern, a medication titration protocol will be recommended, rather than full drug withdrawal, with appropriate monitoring of signs and symptoms. In addition, following the deprescribing intervention, systematic safety assessments and data recording will be done.

Steps Taken to Reduce Risks and Increase Impact of Study: The following are actions to minimize risk for the study population and maximize the impact of this study in deprescribing:

1. Intervention protocols included in this study are supported by a well-grounded conceptual framework, clinical evidence and, although not yet proven, the potential to benefit older person with dementia living in an assisted living facility.

2. The study protocol has been informed by a broad range of expertise including geriatrics, gerontology, pharmacology, LTC nursing and medicine, psychiatry, and implementation science methodologists.
3. Deprescribing actions and decisions will be guided by a clear and explicit protocol that will enable transparency and explanation of results and allow for broader generalizability.
4. The intervention protocol is general in its approach, however all deprescribing decisions are individualized to the patient, after considering the input from the NP expert, the resident, the Abe's Garden care team, and outpatient prescribers.
5. In the event that medications have increased potential for physiologic withdrawal, pharmacokinetic / pharmacodynamics effects, or medical condition exacerbation we will implement a titration protocol to minimize risk.
6. We have designed our trial with weekly follow-up of residents throughout the study period, thus allowing for robust follow-up for any potential adverse drug withdrawal events.
7. All protocols, consent forms, and research materials will have been submitted to the Vanderbilt IRB as part of the pilot intervention and will be approved.

